**diabetes QoL, GM, BP, cholesterol, medication adherence, and diabetes SE, and reduced diabetes distress, PAID, inpatient utilization, unscheduled T2D physician visits and sick days.**

**Primary Analysis for Aim 2.** Our primary outcome, the basis of our sample size calculation, is change in HbA1c for DTM relative to COM from **baseline to 180 days**. We will use the modified Zelen RCF method. For this continuous data, we will use mixed models repeated measures analysis of covariance (ANCOVA) (SAS 9.4; SAS Institute, Cary, NC) to compare the change in pre-post DTM HbA1c with the change in pre-post COM HbA1c, adjusting for caregiver status (Y,N). In keeping with ICH E9 statistical principles for clinical trials (V.7G) with a stratification variable, the interaction term for treatment x caregiver status will be included in the primary analysis, as well as main effects for treatment and caregiver status. Upon finding a significant treatment x caregiver interaction, treatment effects will be estimated separately for those with and without a caregiver (using ANCOVA for unequal slopes).

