transformations will be considered for all analyses. Subgroup analyses are outlined separately below. **Assess data source adequacy.** Given the RCT approach, it is unlikely that demographics will be misrepresented in treatment groups. Thus, confounding is highly unlikely. However, demographic variables such as age, race/ethnicity, and insurance will be easy to measure through self-report, based on the success of an ongoing PCORI trial of telehealth-delivered CHF management (PI: [name]). These data will be a combination of self-report/medical record verification. The primary endpoint, HbA1c, is highly reliable as it is derived from a reputable, licensed laboratory. **Planned sensitivity analyses to determine the impact of key assumptions.** For all analyses, underlying assumptions will be evaluated using SAS diagnostic tools (PROC GENMOD, PROC MIXED, and PROC GLM). **Address missing data.** The best protection against missing data is to prevent it in the first place. To this end: 1) we have already partnered with the clinic directors to ensure that patient records will be available; 2) two separate team members, [name] and [name], will track the completion of data weekly (checking each other's data), which will be reported at weekly research meetings; and 3) each team member will have clearly defined tasks and will regularly report on progress. **Prevention and monitoring of missing data on outcomes:** Participants in both arms will be contacted (DTM through video visit; COM monthly by phone). This will be a "check-in" contact to assess how patients are doing and whether they have interacted with the healthcare system (i.e., ED visits). The RN will make all patient contact. If a patient does not continue with the study, we will ask for the reason for discontinuance. We will ask permission to collect outcome data as scheduled. We believe that this will help obtain outcome data in the spirit of ITT. In addition, we will use our pilot study and focus groups or structured interviews to identify potential challenges to data collection that we can address a priori. During data collection researchers Dr (s) [name] and [name] will assess weekly capture of all outcomes. The database management system, managed by the Biostatistics Unit, includes features that report test and form completion. The study team will monitor data collection and troubleshoot during regular meetings. We will also minimize risk of incomplete data by making surveys as easy as possible for the patient, conducted in their home; we will also perform cognitive pretesting with our PAC and field test surveys with pilot patients. **Statistical methods to handle missing data.** We will use standard methods of multiple imputation. Since HbA1c will be measured 4 times (baseline, 3 months 6 months and 12 months) pre-HbA1c data will necessarily be available and 3 or 6-month data (theoretically) will not. Therefore, a monotone missing data structure will be used. The missing data mechanism will be assumed to be missing at random (MAR). Similar approaches will be used for secondary outcomes-continuous and binary. **Recording and reporting reasons for dropout and missing data, and account for all patients in reports.** We will use the CONSORT diagram method to describe/account for subjects who drop out or for whom outcome variables are missing. Tables will reflect frequency/reasons for missing data. **Sensitivity of inferences to missing data methods and assumptions, and incorporation into interpretation.** A commonly used sensitivity analysis for the MAR assumption in multiple imputation is based on the pattern mixture model approach, modeling distribution of responses as a mixture of observed responses and missing responses. **Goals of planned HTE analyses.** We will evaluate whether the treatment effect in H/L patients with a caregiver participating differs from those that do not by examining the treatment x caregiver status interaction term. Similarly, we will also evaluate whether the treatment effect in female H/L patients differs from male patients by examining the treatment x gender interaction term. It should be emphasized, however, given our resources, there may be insufficient power to detect such interactions. Therefore, these analyses will be exploratory. If feasible, we will also evaluate the treatment x SE interaction. **HTE analysis plan.** In keeping with ICH E9 statistical principles for clinical trials (V.7G), the interaction terms for treatment x caregiver status, and treatment x gender will be included in the primary analysis, as well as main effects for treatment, caregiver, and gender. We plan on exploratory subgroup analyses to explore differential effects of treatment on caregiver

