**SECTION FIVE: SAMPLE SIZE JUSTIFICATION**

Our estimated sample size is 224 patients (240, assuming a 10% attrition rate): 112/group, yielding 80% power to detect a 0.5% difference in the pre-post change in HbA1c (two-tailed t-test with  $\alpha = .05$ ) over 6 months. Our power calculation is based on Polisena et al.'s meta-analysis. We computed a sample size-weighted median of the 12 standard deviations (SD) for HbA1c, yielding a value of 1.2%. If the SD of the pre-post 6-month change in HbA1c is 1.2% in each group, a 0.45% difference in this 6-month change yields a 0.42 effect size (ES). This ES is realistic, falling between 2 sets of reductions in the literature: the Diabetes Control and Complications Trial (1% decline in HbA1c reduced microvascular complications by 30%) and RCTs/meta-analyses citing reductions of 0.3% as "clinically significant". Our reduction of 0.45% falls between those limits, is clinically significant/meaningful, as patients can see improvements in their scores. In a systematic review of 13 RCTs (n=4,207) telehealth was associated with a clinically significant mean HbA1c decline of -0.44% compared to COM. In medically underserved patients, telehealth led to a net improvement in HbA1c, cholesterol, and BP. Although our main power calculation refers to our primary outcome (HbA1c), power is still acceptably high for secondary variables (SE, distress or QoL) such that 112 patients/group will yield 80% power to detect an effect size of 0.4 SDs, using a simple t-test to sample size and power.

Figure 4. Study Plan: Following 240 Patients for 12 Months Randomized to Either DTM (n=100) or COM (n=100) with 6 Month Intervention, Assuming 10% Attrition, Resulting in a Final Sample Size of 200

Year	2019												2020												2021												2022																																																	
Month	1	2	3	4	5	6	7	8	9	10	11	12	13	14	15	16	17	18	19	20	21	22	23	24	25	26	27	28	29	30	31	32	33	34	35	36	37	38	39	40	41	42																																												
Enrollment	CAB Focus Group: Confirm Outcomes, Preliminary Intervention Adaptions & Study Design												PAC Focus Group: Confirm Outcomes, Preliminary Intervention & Study Design Adaptions & Recommendations												Provider Focus Group: Pre-Pilot Adaptation Recommendations												CAB: PAC: Provider Focus Group Analysis												Pre-Pilot Adaptation Approval by the CAB																																					

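### The primary HbA1c model does not name baseline HbA1c as a covariate; read as written it is a change-score comparison, which gives up precision the trial could have at no cost

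*Combined protocol and SAP*

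**What the plan says.** Section 12, Primary Analysis for Aim 2, says that the primary outcome "is change in HbA1c for DTM relative to COM from" baseline to 180 days. For it, "we will use mixed models repeated measures analysis of covariance (ANCOVA") in SAS "to compare the change in pre-post DTM HbA1c with the change in pre-post COM HbA1c", "adjusting for caregiver status (Y,N"). The terms are then listed: "the interaction term for treatment x caregiver status will be included in the primary analysis, as well as main effects for treatment and caregiver status". If the interaction is significant, separate effects are to be estimated with a form of ANCOVA that allows unequal slopes. The variable that would carry the slope is not named.

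The HTE analysis plan in the same section lists the terms again. The treatment-by-caregiver and treatment-by-gender interactions "will be included in the primary analysis, as well as main effects for treatment, caregiver, and gender".

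Under Secondary Analyses for Aim 2, HbA1c over time gets the same kind of repeated-measures ANCOVA, with days 0, 90 and 180 as its time points. Outcomes 4-10 are to use models like the primary one. The missing-data paragraph expects a baseline HbA1c for every patient.

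Section Five sizes the trial with a two-tailed t-test on change. It assumes that the SD of the 6-month change is 1.2%, and gives the source as follows: "We computed a sample size-weighted median of the 12 standard deviations (SD) for HbA1c".

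**The concern.** The response is a change, and the named adjusters are caregiver status and gender. Baseline HbA1c, ordinarily the strongest available predictor of follow-up HbA1c, appears in neither list. A programmer following the text could fit day 0 and day 180 as two responses and report the treatment-by-time contrast. Another could enter day 0 as a covariate. Both would be following the plan, yet they would report different estimates and standard errors.

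What is at stake is precision. A change score fixes the weight on baseline at one, whereas a fitted slope uses the weight that the data support. With a correlation well below one, the change score over-corrects a chance baseline imbalance and has the larger variance. The same form passes to the continuous secondary outcomes.

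**Working it through.** **Inputs from the plan (Section Five).** 112 per arm; two-sided alpha 0.05; SD of change 1.2%; difference 0.45%. The power sentence also gives 0.5%. The 100 per arm used below is stated in Section 12 (1bi, 1bii and Tertiary analyses) and in Figure 4.

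**Assumed.** The correlation rho between baseline and day-180 HbA1c is not given; I use 0.3 to 0.8. Variances are taken as equal at the two times.

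**Step 1: the plan's own figure.** Standardised difference = 0.45/1.2 = 0.375. Noncentrality = 0.375 x sqrt(112/2) = 2.81 on 222 df, which gives 79.8% power by t-test (80.1% by the normal approximation). The stated 80% at 112 per arm reproduces for 0.45%. For 0.5%, about 91-92 per arm would suffice, and power at 112 is 87.4%, so 0.45% is the difference that matches the sample size.

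**Step 2: variances.** With SD s at each time:
- change score: 2s²(1-rho)
- baseline-adjusted: s²(1-rho²)
- ratio, adjusted to change: (1+rho)/2, a saving of (1-rho)/2

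Holding the SD of change at 1.2%, the adjusted residual SD is 1.2 x sqrt((1+rho)/2).

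**Step 3: power for 0.45% (t-test).**

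| rho (assumed) | Residual SD | Variance saved | 112 per arm | 100 per arm |
|---|---|---|---|---|
| change score, any rho | 1.200 | none | 79.8% | 75.1% |
| 0.3 | 0.967 | 35% | 93.4% | 90.5% |
| 0.5 | 1.039 | 25% | 89.7% | 86.2% |
| 0.7 | 1.106 | 15% | 85.8% | 81.7% |
| 0.8 | 1.138 | 10% | 83.8% | 79.4% |

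**Step 4: does the repeated-measures label change this?** In one simulated trial (112 per arm, rho 0.5, complete data), a mixed model with day 0 as a response and free arm means gave a treatment-by-time estimate of -0.2045. The difference in change scores was also -0.2045; ANCOVA with baseline as covariate gave -0.1984. Over 4,000 simulated trials with a true effect of -0.45, the mean estimates were -0.445 (change score) and -0.446 (ANCOVA), so neither is biased. The variance ratio was 0.749, against 0.75 from the formula.

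**Step 5: which SD is 1.2%?** If it were the SD of HbA1c level, the SD of change would be 1.2 x sqrt(2(1-rho)), which equals 1.2% only at rho = 0.5. Change-score power at 112 per arm would then run from 65.6% (rho 0.3) to 95.0% (rho 0.7), and baseline-adjusted power from 83.4% to 97.5%.

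**The case against.** The strongest reply is that baseline may already be intended. The method is called ANCOVA, and unequal slopes need a continuous covariate; caregiver status and gender are binary, so baseline HbA1c is the obvious candidate. The lists are also incomplete, since neither names time or treatment by time, so absence from them does not prove exclusion. Section 11 (Formal Study Protocol) says that detailed analytical methods are still to be written. Day 0 is placed among the repeated measures only for a secondary outcome, and a model with a constrained baseline would recover the precision even there. Sizing by t-test and analysing by ANCOVA is ordinary conservative practice.

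This stands as far as intent goes: one cannot say that the sponsor means to leave baseline out. It does not settle the model. The only adjuster named beside the ANCOVA label is caregiver status, the slope variable is nowhere identified, and the one place that mentions day 0 in such a model treats it as a response.

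Two stronger readings are tempting, and the documents support neither. A reader might infer that the stated power depends on an undisclosed correlation. It does not: Section Five assumes the SD of change directly, so change-score power is 79.8% at 112 per arm whatever rho is. Dependence would arise only if 1.2% is an SD of level (Step 5), which the description of its source leaves open. A reader might also infer that having no HbA1c threshold for entry makes regression to the mean a threat. Selecting on high values is what induces it, and randomisation balances it between arms in expectation.

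It is also fair to say that the gain shrinks to nothing as rho approaches 1, and that (1+rho)/2 rests on equal variances.

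**Conclusion.** The point holds as a gap in specification with a real but moderate cost. Followed as written, the primary analysis most naturally gives a change-score contrast. It is unbiased under randomisation, and it meets the 80% target for 0.45% if 112 per arm are analysed. It forgoes a variance reduction of 10% to 35% for assumed rho of 0.8 to 0.3.

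The margin matters more at 100 per arm. There the unadjusted analysis falls short of 80% for 0.45%, and adjustment restores about 80% or more across the assumed range. At the 0.5% difference also quoted in Section Five, the unadjusted analysis already exceeds 80% at either size (87.4% and 83.4%), and the change would be a gain in precision only.

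The sizes rest on the assumed rho, equal variances at the two times, and 1.2% being the SD of change. This is a recommended improvement, not a defect that invalidates the trial.

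**What to change.** In Primary Analysis for Aim 2, specify day-180 HbA1c (or change to day 180) as the response, with treatment, the stated caregiver terms, and baseline HbA1c as a continuous covariate. A repeated-measures model with day 0 as a response and one baseline mean common to both arms is an equivalent choice; the plan should say which is used. Make the HTE list of primary-model terms agree. Use the same form for the continuous secondary outcomes, each with its own baseline value where one is measured.

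In Section Five, state whether 1.2% is an SD of change or of level; if it is of level, give the correlation assumed.

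The cost is a few sentences. Baseline HbA1c is already collected, and no extra patient, visit or test is needed. The change should be made before outcome data are compared by arm.

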
and gender groups. Upon finding a significant treatment x caregiver interaction (or treatment x gender interaction), the effect of treatment on A1C will be estimated separately for caregiver status (Y/N) (likewise for gender). Estimate of treatment effects and their 95% CI will be constructed. **The basis for all HTE claims based on appropriate statistical contrasts among groups being compared.** The literature and discussions with our CAB indicate the importance of family in the H/L culture. Given the different social/familial roles of women, we will also explore potential gender differences. We will also look at type of caregiver (paid/family) and explore caregiver type in a post hoc analysis to better understand the effect of caregiving. **HTE analysis plan to report all pre-specified analyses and, at minimum, the number of post-hoc analyses, including all subgroups and outcomes analyzed.** With the rich data set expected from this study, we will examine data patterns in an exploratory post-hoc way to identify potential trends not specified a priori. While we will use both exploratory and standard statistical approaches, p values, and associated CIs will be interpreted cautiously, as firm conclusions cannot be drawn. Post-hoc analyses will be adjusted for multiple testing. **Reporting plan to allow for assessments of the study's internal and external validity.** We will report trial results according to the CONSORT guidelines for reporting of RCTs, using the CONSORT 2010 checklist. We will report the progression of patients through the study using the CONSORT flow diagram, showing numbers of patients at each study point (enrollment, allocation, follow-up), and reasons for attrition at each point. For reporting qualitative results, we will use the COREQ a 32-item checklist for interviews/focus groups.

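### Separate caregiver and gender effects on HbA1c are to be estimated only after a significant interaction, so at plausible interaction sizes the difference reported would be overstated on average; report them whatever the p-value

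*Combined protocol and SAP*

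**What the plan says.** In Section 12, Primary Analysis for Aim 2, the model for change in HbA1c always contains treatment, caregiver status and their interaction. The next step is conditional: "Upon finding a significant treatment x caregiver interaction, treatment effects will be estimated separately for those with and without a caregiver".

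The HTE analysis plan, later in Section 12, repeats the rule and extends it: "Upon finding a significant treatment x caregiver interaction (or treatment x gender interaction), the effect of treatment on A1C will be estimated separately". Estimates with 95% CIs are promised directly after that sentence.

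Under Goals of planned HTE analyses the plan warns that "given our resources, there may be insufficient power to detect such interactions", and for that reason calls these analyses exploratory. The Tertiary analyses paragraph also calls subgroup analysis exploratory and says that no literature supports a particular effect size.

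No part of the plan commits to showing caregiver- or gender-specific effects when the interaction is not significant.

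**The concern.** Estimating subgroup effects only after a significant test is a selection rule. When power is low, the test is passed mainly in trials where chance has pushed the two subgroups apart, so the estimates that get reported are on average too far apart. In the remaining trials the plan does not commit to any subgroup estimates.

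Caregiver status matters in this trial. It is the participant subgroup named in Section 7, the caregiver app is one of the seven components that separate DTM from COM, and the caregiver comparison is the first HTE goal listed. Inflating one subgroup and deflating the other is how a false message that the programme works only with a caregiver could arise.

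**Working it through.** **Inputs from the plan** (Section Five, Sample Size Justification, unless stated)
- Size: "Our estimated sample size is 224 patients (240, assuming a 10% attrition rate): 112/group".
- SD: "If the SD of the pre-post 6-month change in HbA1c is 1.2% in each group".
- Planned effect: 0.45% HbA1c. The same paragraph also says 0.5%.
- Caregiver participation: at least 50% (Section 12, item 1bvi).

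**Assumptions, not in the plan**
- Two-sided alpha of 0.05 for the interaction.
- A 50/50 caregiver split in both arms.
- The same SD in all four cells and no variance gain from covariates.
- The true subgroup effects.

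**Step 1: reproduce the sample size.** n per arm = 2 × (1.96 + 0.8416)² × SD² / δ².
- δ = 0.45: 2 × 7.849 × 1.44 / 0.2025 = 111.6, so 112. This matches the plan.
- δ = 0.5: 2 × 7.849 × 1.44 / 0.25 = 90.4, so 91. The stated 112 with 80% power therefore fits 0.45%, which is used below.

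**Step 2: precision.** Each caregiver stratum has 112 × 0.5 = 56 patients per arm.
- SE of each subgroup effect = √(2 × 1.44/56) = 0.227.
- SE of the interaction = √(4 × 1.44/56) = 0.321.
- Smallest significant difference = 1.96 × 0.321 = 0.63% HbA1c, above both 0.45% and 0.5%.

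**Step 3: how often the condition is met, and what is then reported.** For a true interaction θ, let a = 1.96 − θ/SE and b = −1.96 − θ/SE.
- P(significant) = 1 − Φ(a) + Φ(b).
- Mean reported difference = θ + SE × [φ(a) − φ(b)] / P.
- With equal stratum SEs, half of the excess is added to the larger true effect and half is taken from the smaller.

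| True effects (%) | θ | P(significant) | Mean difference if significant | Ratio to θ | Mean subgroup estimates |
|---|---|---|---|---|---|
| 0.55 / 0.35 | 0.20 | 9.6% | 0.70 | 3.5 | 0.80 / 0.10 |
| 0.675 / 0.225 | 0.45 | 29% | 0.83 | 1.84 | 0.86 / 0.04 |
| 0.45 / 0 | 0.45 | 29% | 0.83 | 1.84 | 0.64 / −0.19 |
| 0.90 / 0 | 0.90 | 80% | 1.01 | 1.12 | 0.96 / −0.06 |

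Worked row, θ = 0.20: θ/SE = 0.624, a = 1.336 and b = −2.584. P = 0.0956, and the mean is 0.20 + 0.321 × (0.1634 − 0.0142)/0.0956 = 0.70. The excess of 0.50 splits as +0.25 and −0.25.

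**Step 4: sensitivity.**
- 100 per arm with a 70/30 split: the threshold is 0.73%. θ = 0.45 is significant in 23% of trials, with a ratio of 2.1.
- SD cut to 1.0 by covariates: the threshold is 0.52%. θ = 0.20 is significant in 11.6% of trials.
- 80% power for the interaction at 224 patients needs θ = 2.80 × 0.321 = 0.90, twice the planned effect.

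The plan gives no gender split. At 50/50 the same figures apply, and any other split raises the threshold.

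**The case against.** The strongest reply is that the plan already has most of what is needed: an exploratory label, an open warning about power, 95% CIs, and an interaction term that is always fitted and examined. The HTE plan also mentions exploratory subgroup analyses without attaching a condition, and a nearby heading promises that all pre-specified analyses will be reported.

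The label, the warning and the CIs stand, and they limit the harm. They do not remove the selection: ordinary CIs shown only after a significant test lose their nominal coverage. The unconditional mention is followed at once by the condition, and the heading covers only what the condition has triggered. At best the text is ambiguous about a non-significant interaction.

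A reader might infer more than the documents support, in four ways.
- **That every reported subgroup effect would be grossly exaggerated.** The bias depends on an unknown true interaction and is small at 0.9% or above. The 3.5-fold figure concerns the difference between subgroups. In that scenario the larger effect rises from 0.55 to 0.80 (about 1.45-fold), while the smaller one shrinks.
- **That with no true difference the trial would favour one named subgroup.** With 0.45% in both, the test is significant in 5% of trials. Sorting the estimates by size in each such trial gives averages of about 0.82 and 0.08, but each named subgroup still averages 0.45.
- **That the plan admits it lacks power.** It says only that power may be insufficient.
- **That non-significant results will be suppressed.** The plan does not say so. It gives no commitment either way.

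One further objection stands. Sections 6 and 23 describe asking DTM patients about caregivers, Table 1 gives COM no caregiver app, and the HTE goals define the subgroup by a caregiver participating. The primary analysis refers to a stratification variable, but nothing says how COM patients are classified. Unconditional reporting alone would not cure that.

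**Conclusion.** The point holds in a limited form. As written, the rule ties separate caregiver and gender estimates to a test that needs about a 0.63% HbA1c difference. For true interactions up to the size of the planned effect, that test succeeds in at most 29% of trials, and the difference then reported is overstated by 1.8-fold or more on average. The distortion fades to about 1.1-fold at 0.9%.

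These figures rest on 112 per arm, SD 1.2%, an even caregiver split in both arms and a two-sided 0.05 interaction test. Fewer patients or an uneven split makes matters worse; a variance gain from the repeated-measures ANCOVA lessens the problem. The analyses are already labelled exploratory, so this is a defect in a reporting rule, worth correcting because the correction is nearly free.

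**What to change.** Replace the conditional sentences in Primary Analysis for Aim 2 and in the HTE analysis plan with one statement: the interaction estimate and the treatment effects on HbA1c by caregiver status and by gender, each with a 95% CI, will be reported whatever the interaction p-value; they are exploratory, and no subgroup claim will be made from a significance test.

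State also how and when caregiver status is recorded. It must be classified the same way in both arms before randomisation for the caregiver estimates to be valid comparisons.

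The reporting change costs SAP wording and a forest plot, with no extra patients or alpha. It removes the selection but not the imprecision: under the same assumptions the 95% CIs would be about ±0.44% for each subgroup effect (1.96 × 0.227) and ±0.63% for the interaction. If caregiver status is not already collected at baseline in COM, one question before randomisation would be needed.
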